4.7. Sample size

In October 2021, a revised sample size calculation was performed, based on the study shortening from 22 months to 14 months (plus a 2-month transition period). As part of this, using data from the accrued baseline period (collected from October 2020 to September 2021), we estimated some of the parameters assumed in the earlier sample size and power calculations. The revised sample size calculation was made based on empirical baseline data from clusters being included in the trial.

Below, we describe the methods used to calculate the sample size.

The original estimates of the parameters required for the sample size calculation are described, alongside updated estimates based on the data from the baseline period. Full details of the original sample size calculation can be found in the protocol.

Assuming there are 80 health facilities in the trial, evenly split across the intervention and control groups, with an average number of 192 births per cluster per month, the anticipated total sample size for the study (running for 14 months) would be 215,040 ($=80*192*14$). The number of health facilities (80) has been inflated by 10% to allow for dropout from the number of health facilities required (72).

In the control condition, we initially expected the prevalence of the primary composite outcome to be around 2%. This prevalence is informed by the prevalence of a similar outcome based on the analysis of the CHAMPION trial, a large multi-country study of PPH prevention[4]. We considered sensitivity to this prevalence between 1.5% and 4%. Analysis of the baseline data from E-MOTIVE clusters, however, found a prevalence of the primary outcome of 3.6% (95% CI: 3.4% to 3.8%).

A relative risk reduction of 25% was considered to be a clinically meaningful difference to detect, though smaller reductions could also be worthwhile. Under some scenarios (such as a high value of the ICC) this target effect size might not be detectable at 90% power. We have thus considered sensitivity to the power for a relative reduction of 20% and 30%.

Sample size calculations have allowed for the clustered nature of the design through the intra-cluster correlation (ICC). As recommended, values for the ICC have been informed through a combination of the literature and analysis of available data on a similar set of outcomes. Analysis of the CHAMPION trial found an ICC of 0.03 (95% CI: 0.02 to 0.05) for a similar composite outcome of PPH \geq 1000 ml, laparotomy and maternal death. This ICC was estimated using a linear mixed regression model and so is on the proportions scale as is appropriate for a sample size calculation. As the literature suggests, rare clinical outcomes tend to have small ICCs, for this reason, we have considered an extended range for the ICC,

from 0.001 to 0.05, with an expected ICC of 0.02. Analysis of the baseline data from the E-MOTIVE clusters found an ICC of 0.018 (95% CI: 0.01 to 0.034).

To allow for variations in clustering over time, we have allowed for a cluster-by-period random effect. This has been incorporated in the sample size calculations using the cluster autocorrelation (CAC). There is limited information from the literature on the likely values of the CAC. Using data from the CHAMPION trial, we created two 7-month periods, which match the planned study design. From this, we estimated a CAC of 0.97. No current methodology exists to calculate a confidence interval for this value. We have chosen to consider sensitivity to the CAC between the values of 0.95 and 1.0. No estimate of the CAC could be made using the accrued baseline data.

Appendix Table E7 provides information on the expected levels of power for a 14-month study (two 7-month periods) across the range of parameters described above. These suggest that the study has at least 90% power at 5% significance (two-sided) to detect a 30% RRR for most scenarios after allowing for clustering and varying cluster sizes. The study will have over 90% power to detect smaller RRR if the ICC is close to the lower bound (0.001), the CAC is at the upper bound (1.0), or the prevalence of the study is relatively large (4.0%).

With large prevalence (4.0%), the study would have over 90% power to detect a 20% RRR for most likely scenarios (Appendix E7). A re-estimation of the CAC using two 7-month periods in the CHAMPION trial data found a CAC of 0.99. With a CAC of 1.00, the study would have over 90% power to detect a 20% RRR for most likely scenarios.

4.8. Interim analyses and stopping guidance

Arrangements for Data Monitoring Committee (DMC) oversight has been agreed, and details can be found in the DMC Charter.

4.9. Internal Pilot Progression Rules

Not Applicable

4.10. Timing of final analysis

The final analysis for the trial will occur after all clusters have been randomised, ran for a fixed period of time post-randomisation (7-months, and the corresponding outcome data have been entered onto the trial database and validated as being ready for analysis. This is provided that the trial has not been stopped early for any reason (e.g., DMC advice to TSC or funding body request).

4.11. Timing of other analyses

Not applicable

4.12. Trial comparisons

All references in this document to 'group' refer to E-MOTIVE or usual care.

5. Statistical Principles

5.1. Confidence intervals and p-values

All estimates of differences between groups will be presented with two-sided confidence intervals of appropriate size.

As described earlier, the outcomes can be grouped in to four categories: the primary outcome; the key implementation outcomes; secondary clinical outcomes; and secondary implementation outcomes. See section 4.5 and 4.6 for details of the outcomes. P-values will be reported for the primary outcome only. For all other outcomes (key implementation, secondary clinical and secondary implementation), we will not present p-value unless requested to by a peer reviewer. To this end, summary measures with 95% confidence intervals will be presented as supporting evidence only, and should be cautiously interpreted due to the possibility of multiplicity. For clarity, the information presented for each outcome group is highlighted below.

Primary Outcome

We will report the number of patients in each group (E-MOTIVE or usual care) stratified by time-period, the summary measure, and a two-sided 95 % confidence interval. Hypothesis testing will be carried out at the (two-sided) 5% level of significance. A p-values will be reported for the primary outcome.

Key implementation outcomes

We will report the number of patients in each group (E-MOTIVE or usual care) stratified by time-period, the summary measure, and a two-sided sided 95 % confidence interval. We will not report p-values for secondary outcomes, unless requested by external statistical reviewer(s).

Secondary clinical outcomes

We will report the number of patients in each group (E-MOTIVE or usual care) stratified by time-period, the summary measure, and a two-sided sided 95 % confidence interval. We will not report p-values for secondary outcomes, unless requested by external statistical reviewer(s).

Secondary implementation outcomes

We will report the number of patients in each group (E-MOTIVE or usual care) stratified by time-period, the summary measure, and a two-sided sided 95 % confidence interval. We will

not report p-values for secondary outcomes, unless requested by external statistical reviewer(s).

5.2. Adjustments for multiplicity

No correction for multiple testing will be made.

For all secondary clinical and implementation outcomes (see section 4.6), results will be interpreted with caution due to the potential for multiplicity issues.

5.3. Analysis populations

All primary analyses (primary and secondary outcomes including safety outcomes) will be by intention-to-treat (ITT) with appropriate adjustment for clustering. Patient and clusters will be analysed in the group to which they were randomised, and all patients (and clusters) shall be included whether or not they received the allocated intervention.

6. Trial population

6.1. Cluster Inclusion Criteria

Health facilities (clusters) are eligible for inclusion if they have 1000 to 5000 births a year and provide comprehensive obstetric care with ability to perform surgery for PPH. Clusters are selected based on being administratively and geographically distinct from each other. Pre-existing implementation of early detection or bundled approach for PPH management are exclusion criteria.

The cluster start date for inclusion in the study, is the date in which $\geq 80\%$ of their patients have source data verification.

6.2. Research Participant Inclusion Criteria

All healthcare providers attending vaginal births at the study facilities.

6.3. Patient Inclusion Criteria

All women who have a verified vaginal birth in the included health facilities. A woman with a verified vaginal birth is a woman for whom we have patient and birth information.

6.4. Cluster and participant flow

A flow diagram (as recommended by CONSORT[5]) will be produced to describe the participant and cluster flow through each stage of the trial. An example of how this may look is presented in Appendix E1. In this trial, clusters are recruited, but there is no participant recruitment (all eligible patients are included in the study).

Cluster flow

We will present the number of clusters recruited, the number of clusters that were randomly assigned, the number (with reasons) of any clusters lost to follow-up (drop-outs and withdrawals), and the number that were analysed for the primary outcome and key implementation outcomes.

Participant flow

We will present the number of patients meeting the inclusion criteria in the baseline period and the post-randomisation period, as well as the number of patients that were analysed for the primary outcome and key implementation outcomes.

CRTs are prone to a variety of biases, depending on recruitment processes, timing of recruitment, and whether blinding occurs. To improve clarity of the timing of the trial processes and blinding, which are not covered by reporting guidelines, we will use the timeline cluster graphical tool to clarify the processes used here and to identify potential bias in the study[6]. An example is presented in Appendix E2.

6.5. Baseline characteristics

Characteristics of the health facilities and the individual patients will be summarised as per Appendix E3.

We will tabulate the characteristics of the health facilities, stratified by allocation to E-MOTIVE or control, and stratified by time-period (baseline or post-randomisation), and present the number of facilities in each group, with percentages.

We will tabulate the characteristics of included patients, stratified by allocation to E-MOTIVE or control, and stratified by time-period (baseline or post-randomisation). Categorical data will be summarised by number of patients, counts and percentages. Continuous data will be summarised by the number of patients, mean and standard deviation if deemed to be normally distributed, or number of patients, median and interquartile range if data are skewed, and ranges if appropriate. For the main trial report, tests of statistical significance will not be undertaken, nor confidence intervals presented[7], unless requested by external statistical reviewer(s).

7. Analysis methods

The study's primary aim is to evaluate whether there is a difference in the primary composite outcome in the intervention group (E-MOTIVE) compared to the control group.

Below, we present the model choice and analysis methods for the primary outcome, the secondary clinical outcomes and the secondary implementation outcomes. We present methods for accounting for clustering and methods for dealing with model non-convergence. We present the plan for adjusting for covariates and describe the sub-group and sensitivity analyses.

In summary, we will be comparing E-MOTIVE and the control using a constrained baseline analysis, as recommended by Hooper et al[8]. Mixed-effect regression models are fitted to the data, with a random effect to allow for clustering, and random cluster-period effect to allow the correlation between observations within a cluster to vary if the observations are made at different time periods. Fixed effects are included for time-period, allocated exposure to E-MOTIVE, and covariates used in the randomisation. The covariate representing allocated exposure to E-MOTIVE will indicate the impact of E-MOTIVE.

The analysis of the primary outcome is described in sections 7.4. The analysis of secondary clinical and implementation outcomes is described in sections 7.5.

See Appendix D for information on how variables will be derived for the analysis. A template for reporting the primary outcome is given in Appendix E4, and the secondary clinical and implementation outcomes in E5.

7.1. Estimands

Since E-MOTIVE is a cluster trial, the summary measure of the effect of E-MOTIVE can be measured in different ways. That is to say, the unit of inference of whether the treatment is beneficial can be made at the unit of randomisation (cluster) or at the unit of data collection (participant). Please see Appendix E8 for further information.

In E-MOTIVE, for all outcomes (both clinical and implementation), we will be estimating the participant-average summary measure. This will indicate the average summary measure across patients, that is, how effective E-MOTIVE is for the average participant. See sections 7.4 for details on the analysis methods.

The list of clinical outcomes and implementation outcomes is given in section 4.6.

7.2. Informative cluster sizes

In cluster trials, the choice of analysis method is influenced by whether there are informative cluster sizes – which is when the size of a cluster is associated with the outcome in that cluster[9]. This could be because the outcome rate differs between small and large clusters, or because the summary measure differs between small and large clusters. In E-MOTIVE, it is plausible that there may be informative cluster sizes, and the analysis methods proposed below contain an adjustment for cluster size, in an aim to account for this. We will also fit generalised estimating equations with independent working correlation matrix as a sensitivity analysis (see section 7.11)[9].

7.3. Summary Measures

For all binary outcomes – this includes the primary composite outcome, the key secondary implementation outcomes, and other secondary clinical and implementation outcomes, we will summarise the number of patients who experience the outcome, and the percentage of the group this corresponds to. Summary statistics will be presented stratified by trial arm (E-MOTIVE or control) and time-period (baseline phase or post-randomisation phase). To quantify the effect of E-MOTIVE, the intervention effect will be presented using relative risk and risk differences – as per CONSORT recommendations³.

For secondary outcomes that are continuous, we will summarise using means and standard deviations or medians and inter-quartile ranges as appropriate. Histograms will be produced to determine which summary statistic is most appropriate. We will present summary statistics stratified by trial arm (E-MOTIVE or control) and time-period (baseline phase or post-randomisation phase). To quantify the effect of E-MOTIVE, the intervention effect will be presented using the mean difference (difference in means between E-MOTIVE and usual care).

7.4. Primary outcome analysis

The model being fitted to the binary primary composite outcome will be a mixed-effect logistic regression model with robust standard errors.

To account for clustering, random effects (for cluster and cluster-period) are included (see section 7.4.1). We will account for the time-period using fixed-effects (see section 7.4.2), and will adjust for covariates used in the randomisation in the first instance (see section 7.4.3). If there are issues with model-convergence, then a plan is in place (see section 7.4.4).

Risk ratios and risk differences will then be derived using marginal standardisation [10], as in for example a CRT by Kirkwood et al [11]. Under this approach, the mean risk under the control condition and intervention condition is obtained. The risk ratio is then derived using the mean risk in intervention condition and by the mean risk in the control condition, with the calculation

being performed on the log scale. The risk difference is derived as the mean risk in intervention condition minus the mean risk in the control condition. We will use the unconditional standard errors to obtain the confidence interval, as this allows for correlation amongst the observations [12].

A small sample correction will not be included in the main analyses as the number of clusters is expected to be sufficiently large to maintain the type I error rate [13].

The integration method used will be mean-variance adaptive Gauss-Hermite quadrature, which is the default in Stata.

7.4.1. Accounting for clustering of observations

To allow for correlation between observations within a cluster, we will fit mixed-effect logistic regression models with robust standard errors. Clustering will be allowed for in all analyses through the use of random effects. Recent developments in the methodological literature for the design and analysis of multiple-period cluster randomised trials suggest that a simple exchangeable correlation structure is not sufficient to depict the correlation structure in multiple-period cluster randomised trials [8]. We will include a random cluster by period interaction in addition to a random cluster effect to allow for the decay in correlation between observations made in the same cluster, but at different time periods.

7.4.2. Primary outcome - accounting for baseline period

The analysis will use a constrained baseline analysis approach, as recommended by Hooper et al[8]. Here, outcomes collected during the baseline period and the post-randomisation period are treated as longitudinal and a repeated measures analysis is used to estimate the summary measure.

Under this approach, there are two binary covariates included as fixed effects in the model: (i) period and (ii) exposure to E-MOTIVE. These covariates are described below.

Covariate for period

A binary variable will indicate whether observations are taken from the baseline period (0) or the post-randomisation period (1) of the study.

Covariate for exposure to E-MOTIVE

A binary 'treatment' variable will indicate whether observations are exposed to the E-MOTIVE bundle. That is, observations taken in the post-randomisation period in clusters allocated to E-

MOTIVE will have a value of 1, and all other observations (control clusters and E-MOTIVE clusters during baseline phase) will have a value of 0. This binary treatment variable will be used to determine the impact of the intervention. Under this approach, it is assumed that there is no systematic differences between the groups at baseline.

7.4.3. Primary outcome – covariate adjustment

In the first instance, the analysis will contain an adjustment for the minimisation parameters listed in section 4.3. Randomisation was performed stratified by country, and so country will also be included as a covariate. However, whilst the number of intervention and control clusters was included in the minimisation, we will not adjust for the number of clusters allocated to E-MOTIVE or usual care.

The number of vaginal births will be modelled as binary (above or below median). Oxytocin quality will be treated as binary (high quality or low quality). Country will be treated as categorical (Kenya, Nigeria, South Africa, or Tanzania).

For the analysis of the primary outcome, we will not include a term for cluster-level primary outcome rate at baseline, as although this was included as a randomisation covariate, the constrained baseline analysis method includes individual-level primary outcome values from the baseline period.

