4.3. Randomisation

After regulatory approvals, 78 clusters from Kenya, Nigeria, South Africa and Tanzania will enter a 7-month baseline period in which they will be following usual care with dissemination of the current guidelines. After this 7-month baseline period, we will allocate 78 clusters (a 1:1 ratio) to either the E-MOTIVE intervention or usual care for 7 months, with an allowance of two months ('transition phase') for full implementation and embedding of the intervention. Clusters not allocated to E-MOTIVE will continue to follow usual care as per the baseline period for the remainder of the intervention phase.

The recruitment of all clusters will be completed within a 3-month period. Following the baseline period, randomisation will be implemented using a minimisation algorithm to ensure a balance of the intervention and control facilities for the following (measured at the cluster-level during the first 5 months of the baseline phase):

1. Number of vaginal births
2. Proportion of births with the composite primary outcome (before randomisation)
3. Oxytocin quality
4. Number of intervention and control clusters in each country

Details of how these are calculated are presented below. The minimisation will be stratified in each country (separate minimisations) to increase the balance in all of the above covariates within a country.

Number of vaginal births

After the first five months of the baseline phase has completed, for each cluster, we will gather the total number of births and the number of months of data collection to calculate the cluster's monthly birth rate. We will then use the cluster's monthly birth rate to determine the country's median birth rate. The clusters above and below the country median will form the categories for the minimisation algorithm.

The proportion of births with the composite primary outcome before randomisation

After the first five months of the baseline phase has completed, for each cluster, we will gather the total number of births and the total number of events. The ratio of the number of events to the number of births will give us the proportion of births with the composite outcome for that cluster. We will then use the cluster's primary outcome proportion to determine the country's median primary outcome proportion. The clusters above and below the country median will form the categories for the minimisation algorithm.

Oxytocin Quality

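### Randomisation is stratified by country, but the primary model carries country only as a main effect with one common period term, so country differences in trend would leave the primary interval modestly wider than the design requires

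*SAP*

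**What the plan says.** SAP 4.3 runs the allocation country by country: "The minimisation will be stratified in each country (separate minimisations"). It also states that "we will allocate 78 clusters (a 1:1 ratio) to either the E-MOTIVE intervention or usual care for 7 months", and the number of facilities per arm in each country is itself a minimisation factor.

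For the primary model, SAP 7.4.2 says "there are two binary covariates included as fixed effects in the model: (i) period and (ii) exposure to E-MOTIVE". SAP 7.4.3 adds country because allocation was stratified by it ("Randomisation was performed stratified by country, and so country will also be included as a covariate"), in this form: "Country will be treated as categorical (Kenya, Nigeria, South Africa, or Tanzania"). SAP 7.4.1 handles change over time within facilities by random effects: "We will include a random cluster by period interaction in addition to a random cluster effect". The model is a "mixed-effect logistic regression model with robust standard errors", and "A small sample correction will not be included in the main analyses".

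No country-by-period fixed effect appears in SAP 7.4, among the sensitivity analyses of SAP 7.11, or in Protocol 11.2, which also describes one binary time indicator. The country subgroup analysis in SAP 7.10 adds only a treatment-by-country interaction.

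**The concern.** The SAP accepts that the analysis should reflect the stratification, but the chosen term reflects only each country's level. With a baseline period and a high CAC, level largely drops out of a facility's change. What the stratified allocation balances, and what still matters, is each country's change over time.

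If usual-care rates move differently in the four countries, each country's shift falls about equally on both arms and mostly cancels from the effect estimate. The model has no term for it, so it is counted as facility-by-period noise. Robust standard errors do not help, because the same shift sits in the residuals. The reported interval is then wider than the estimator's true variability. At stake is the precision of the primary estimate and of the secondary estimates that copy the model.

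Different trends are plausible. Training, facility management and monitoring run through country hubs (Protocol 9.1, 9.2). A facility's start date depends on when it reaches 80% source verification (SAP 6.1), so the same period can cover different calendar months in different countries.

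**Working it through.** **Inputs from the documents.** 78 facilities allocated 1:1, so 39 per arm (SAP 4.3); baseline risk 3.6%, ICC 0.018, CAC 0.97 or 0.99, planned CAC range 0.95 to 1.0 (SAP 4.7); 192 × 7 = 1,344 births per facility-period and cluster-size CV 0.5 (note to the SAP power table).

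**Assumptions.** Countries of 20, 20, 20 and 18 facilities; near-equal arms within country; the share f of temporal variation that is due to country.

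**1. The plan's own power figure** (72 facilities, 4% to 3%, ICC 0.02, CAC 0.97).
- m' = 1,344 × (1 + 0.5²) = 1,680, and 1 + 1,679 × 0.02 = 34.58.
- r = 1,680 × 0.02 × 0.97 / 34.58 = 0.9425. Design effect = 34.58 × (1 − 0.9425²) = 3.86.
- Variance = (0.04 × 0.96 + 0.03 × 0.97) / (36 × 1,344) × 3.86 = 5.39 × 10⁻⁶, so SE = 0.00232.
- 0.01 / 0.00232 − 1.96 = 2.35, giving power 99.1%, as tabulated. All 81 cells reproduce within 1.0 point.

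The formula has no country term. It treats all temporal variation as noise, as the planned model does.

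**2. What the country main effect gains.** The variance of the constrained baseline estimator is proportional to B(2C + B)/(C + B). C is the persistent between-facility variance; B is the facility-period plus sampling variance.
- Log-odds scale: between-facility variance V = 0.018 / (0.036 × 0.964) = 0.519. Sampling variance per facility-period = 1 / (1,344 × 0.0347) = 0.0214.
- At CAC 0.97, C = 0.503 and B = 0.0156 + 0.0214 = 0.0370, so (2C + B)/(C + B) = 1.93.
- If half of C lies between countries, C falls to 0.252 and the ratio to 1.87. The SE falls by 1 − √(1.87/1.93), about 1.6%.

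Over CAC 1.0 to 0.95 the gain is 0.3 to 0.7% if a quarter of the between-facility variance lies between countries, 0.9 to 1.9% if half does, and 2.6 to 5.1% if three quarters does.

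**3. What country trends add, with overall CAC held at the documents' values.** The variance of a facility's change is T + S, where T = 2(1 − CAC)V and S = 2 × 0.0214 = 0.0429. At CAC 0.97, T = 0.0311 and SE = √(0.0740 × 2/39) = 0.0616. Country-by-period terms remove the country part, so

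SE ratio (planned / with the terms) = √[(T + S) / ((1 − f)T + S)].

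| Overall CAC | T | f = 0.25 | f = 0.50 |
|---|---|---|---|
| 0.95 | 0.0519 | 1.076 | 1.173 |
| 0.97 | 0.0311 | 1.057 | 1.125 |
| 0.99 | 0.0104 | 1.025 | 1.053 |

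With only four countries, the common period term absorbs their mean trend, leaving on average about three quarters of the country variance. The largest entry then becomes √[(0.0259 + 0.75 × 0.0259 + 0.0429) / (0.0259 + 0.0429)] = 1.13. Simulation with four countries and unequal facility sizes gave a planned SE about 5 to 15% larger (1.06 to 1.12 times at CAC 0.97). Planned coverage was 93 to 96%, and the estimator's true SD barely changed.

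**4. Where much larger ratios come from.** Simulation (1,000 runs per cell, Gaussian model on facility-period log-odds) with country trends of SD τ added on top of the stated CAC:

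| Stated CAC, τ | Robust SE, planned / with terms | Ratio | Type I error, planned | Overall CAC = 1 − [2(1 − CAC)V + τ²]/(2V) |
|---|---|---|---|---|
| 0.97, 0.2 | 0.0695 / 0.0563 | 1.23 | 3.8% | 0.931 |
| 0.97, 0.3 | 0.0817 / 0.0565 | 1.45 | 1.6% | 0.883 |
| 0.99, 0.2 | 0.0637 / 0.0484 | 1.32 | 2.3% | 0.951 |
| 0.99, 0.3 | 0.0773 / 0.0485 | 1.59 | 1.0% | 0.903 |

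Three of the four rows fall below the planned CAC range. The other sits at its lower limit and needs country to supply 0.04 / 0.0504 = 79% of all temporal variation. Even in these rows, power for an odds ratio of 0.75 under the planned model is 96% or more.

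**5. Coverage with the added terms.** In the runs of step 3, coverage was about 92 to 94% with the planned z reference and about 94 to 95% with a degrees-of-freedom-corrected t reference. With 11 fixed effects (intercept, period, exposure, births, oxytocin, three country, three country-by-period), df = 78 − 11 = 67. The t quantile alone (1.996 against 1.960) widens the interval by only 1.8%. Scaling the SE by √(78/67) = 1.08 does more.

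**The case against.** The plan already includes the stratification factor, uses a recognised constrained baseline model and agrees with Protocol 11.2. The CAC was estimated in a ten-country trial with no stated removal of country trends, so it may already contain them; adding trends on top counts them twice. The error is conservative and the planned power is ample. Adding terms under an uncorrected z reference could replace a slightly wide interval with one that under-covers.

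Most of this stands, and it sets the size of the point. It does not remove the gap: variation balanced by design is still charged to the standard error. Nor does the coverage argument defeat the remedy. With no trend differences, the planned and extended models under-cover about equally (92.6% and 92.2% at CAC 0.97 in one simulation), so the uncorrected reference is the main cause. SAP 7.10 already uses a t correction for cluster-level subgroups.

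A reader might infer that the interval is 20 to 60% too wide, or that the test runs near 1%. That needs country trends of SD 0.2 to 0.3 beyond the planned CAC, which the documents do not support. A reader might also infer lost power. The stated power credits no gain from stratification, so there is nothing to fall short of. Nor is the country main effect worthless; its gain is small, not zero.

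**Conclusion.** The point holds as a modest loss of precision. With overall CAC at 0.95 to 0.99 and a quarter to a half of temporal variation due to country, the planned standard error is about 3 to 15% larger than with country-by-period terms. This rests on assumed country sizes, near-balance of arms within country (minimisation with a 10% random element makes this likely, not exact), the assumed share f, and a Gaussian approximation to the planned logistic model on the log-odds scale. If trends do not differ by country, nothing is lost under the plan and the added terms cost essentially nothing in precision. Validity of the primary test is not threatened from this source.

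**What to change.** - **Primary model (SAP 7.4.2 and 7.4.3).** Add country-by-period fixed effects (three parameters), keeping the single exposure term. Use a t reference with a degrees-of-freedom correction of the kind in SAP 7.10, and state whether the standard error is also scaled, since the quantile alone does little.
- **Non-convergence (SAP 7.4.4).** Drop the country-by-period terms before the cluster-period random effect.
- **Secondary outcomes (SAP 7.5).** Apply the same to common outcomes only. Rare ones such as laparotomy and death may have empty country-period cells.
- **Alternative.** If the sponsor keeps the primary model, list this model, with its correction, as a pre-specified sensitivity analysis in SAP 7.11.

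The cost is a few lines of SAP text, three more parameters among 78 facilities and a slightly wider reference distribution.
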